# 9.1.2.12 Glucose Counter-Regulation

## Rationale:

Islet transplantation is being evaluated as a potential therapy for patients with T1D experiencing severe problems with hypoglycemia. These problems result from the defective glucose counterregulation present in these patients. Recent work has demonstrated normal suppression of endogenous insulin secretion during hypoglycemia and significantly greater glucagon secretion during hypo- when compared to euglycemia in islet transplant recipients. The presence of less endogenous insulin and more glucagon should increase endogenous glucose production by the liver and serve to prevent or correct low blood glucose. Additionally, some islet transplant recipients have normal epinephrine responses to hypoglycemia, which may contribute to increasing glucose production. Because increasing endogenous glucose production is the final common pathway for these hormonal responses and is what is clinically important in the defense against hypoglycemia (not the levels of the hormones themselves), we propose to evaluate endogenous glucose production in T1D patients before and > 6 months following islet transplantation using a hyperinsulinemic hypoglycemic clamp and a paired hyperinsulinemic euglycemic clamp.

#### Approach:

Hyperinsulinemic hypoglycemic clamp: Subjects will avoid strenuous exercise for 3 days prior to testing. On the day before testing, the last injection of long-acting insulin will occur either that morning or the night before. Subjects will be admitted to the General Clinical Research Center (GCRC) of the University of Pennsylvania in the afternoon and fed a standard diabetic dinner with their last injection of rapid acting insulin by 1800 and fasting started at 2000. At 2100 an antecubital venous catheter will be placed for the infusion of regular insulin (0.5 U/mL solution) as needed overnight to maintain the blood glucose between 100 – 140 mg/dL. Any CSII will be discontinued at that time. At 600 a contralateral retrograde venous hand catheter will be placed and the hand warmed in a thermoregulated box (~ 50 °C) for arterialized venous blood sampling. Patency of the intravenous catheters will be maintained with slow infusions of 0.9% saline.

At 0700 (t = -120 min) a primed (5 mg/kg · fasting glucose/90 for 5 min) continuous (0.05 mg/kg·min for 355 min) infusion of  $6.6^{2}$ H2 glucose (99% enriched; Cambridge Isotopes

Laboratories, Andover, MA) will be administered to assess endogenous glucose production before and during the induction of hypoglycemia  $^{166}$ . After baseline blood samples at t = -20, - 10, and -1 min, at 0900 (t = 0 min) a continuous (1.0 mU/kg·min for 240 min) infusion of insulin will be administered to produce hyperinsulinemia. Subsequently, a variable rate infusion of 20% glucose will be initiated to achieve hourly glucose plateaus of 80, 65, 55, and 45 mg/dL. To reduce changes in plasma enrichment of 6,6  $^2$ H2 glucose during the clamp, the variable glucose infusion will be enriched to ~ 2.0 % with 6,6  $^2$ H2 glucose  $^{166}$ .

Blood samples will be taken every 5 min, centrifuged, and measured at bedside with a portable glucose analyzer (YSI 1500 Sidekick; Yellow Springs Instruments, Yellow Springs, OH) to adjust the glucose infusion rate and achieve the desired glucose concentration. Additional blood samples will be taken at t = 20, 40, 60, 80, 100, 120, 140, 160, 180, 200, 220, and 240 min for biochemical analysis and verification of the glucose levels. The total amount of blood sampled will not exceed 168 mL. A questionnaire will be administered every 20 min during the study in order to quantitate autonomic symptoms as the sum of scores ranging from 0 (none) to 5 (severe) for each of the following symptoms: anxiety, palpitations, sweating, tremor, hunger, and tingling  $^{167}$ .

Hyperinsulinemic euglycemic clamp: Because hyperinsulinemia inhibits endogenous insulin secretion, glucagon secretion, and endogenous glucose production, a euglycemic clamp will be performed to assess the impact of insulin per se on endogenous glucose production independent from hypoglycemia. Subjects will undergo the euglycemic clamp in randomized order with the hypoglycemic clamp at least 1 week but not longer than 1 month apart. The hyperinsulinemic euglycemic clamp will be conducted as described for the hypoglycemic clamp above, but with the target glucose 90 mg/dL for the entire 240 min study.

Biochemical analysis: Blood samples will be collected on ice into chilled tubes containing EDTA with protease inhibitors added to protect islet hormones, centrifuged at 4 °C, separated, and frozen at -80 °C within 60 min of collection for subsequent analysis. Glucose will be measured in duplicate by the glucose oxidase method using an automated glucose analyzer (YSI 2300; Yellow Springs Instruments). Plasma immunoreactive insulin, C-peptide, glucagon, growth hormone and cortisol will be measured in duplicate by double-antibody radioimmunoassay (Linco Research, St. Charles, MO) performed at the Diabetes Endocrinology Research Center of the University of Pennsylvania. Plasma epinephrine and norepinephrine will be measured by high-performance liquid chromatography with electrochemical detection at the GCRC laboratory of the University of Pennsylvania. Enrichment of 6,6 H2 glucose will be measured by gas chromatography-mass spectrometry analysis at Metabolic Solutions, Inc. (Nashua, NH). Samples from paired euglycemic-hypoglycemic experiments for each subject will be assayed simultaneously.

*Calculations:* Incremental C-peptide, glucagon, growth hormone, cortisol, epinephrine, norepinephrine, autonomic symptom, and endogenous glucose production responses will be calculated by subtracting basal values from those obtained during the last 20 min of hypo- or euglycemia.

Basal rates of endogenous glucose production (EGP) will be calculated using the formula: basal EGP = IR ([enrichmentinf/enrichmentplasma] – 1), where IR is the basal  $6.6^{2}$ H2 glucose infusion rate in mg/kg·min, enrichmentinf is the percent enrichment of the  $6.6^{2}$ H2 glucose infusate, and enrichmentplasma is the percent basal plasma  $6.6^{2}$ H2 glucose enrichment.

The rate of appearance (Ra) of glucose during the clamps will be calculated using Steele's non-steady state equation modified for the use of stable isotopes: Ra = F-(V[((C2+C1)/2)][(E2-E1)/(t2-t1)]/(E2-E1)/2) where C2 and C1 are the glucose concentrations at the times (t) 2 and 1

respectively; V is the effective volume of distribution of glucose (40 mL/kg), F is the infusion rate (0.05 mg/kg·min), and E represents the isotopic enrichment at the respective time points. EGP during the clamps will be calculated from the difference between the rate of appearance of glucose in the plasma and the glucose infusion rate.

The difference in the incremental responses obtained during the hypo- and euglycemic experiments will be compared within subject from before to after islet transplantation with one-way or repeated measures ANOVA as appropriate with significance considered at P < 0.05 (two tailed).

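### The printed clamp equation for glucose rate of appearance cancels the tracer enrichment, gives negative rates at every clamp target, and contradicts the basal formula beside it (exploratory endpoint only)

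*Protocol*

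**What the plan says.** Protocol section 9.1.2.12 (Glucose Counter-Regulation) plans paired hypoglycemic and euglycemic clamps with a labelled-glucose tracer. Under Calculations it names Steele's non-steady-state equation, adapted for stable isotopes, and prints "Ra = F-(V[((C2+C1)/2)][(E2-E1)/(t2-t1)]/(E2-E1)/2", closing the outer bracket after the final 2. It fixes two of the terms by value: "V is the effective volume of distribution of glucose (40 mL/kg), F is the infusion rate (0.05 mg/kg·min". For the tracer measurement, which should carry the information, it says that "E represents the isotopic enrichment at the respective time points". Clamp EGP is then Ra less the glucose infusion rate.

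Just above, the basal rate is given as "basal EGP = IR ([enrichment inf /enrichment plasma ] – 1", where IR is the same basal tracer infusion.

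The Approach text supplies the other inputs. The hypoglycemic clamp is to "achieve hourly glucose plateaus of 80, 65, 55, and 45 mg/dL". The euglycemic clamp runs "with the target glucose 90 mg/dL for the entire 240 min study". Analytical samples fall at "t = 20, 40, 60, 80, 100, 120, 140, 160, 180, 200, 220, and 240 min". The constant tracer infusate is "99% enriched; Cambridge Isotopes", and the variable glucose infusion is itself enriched with the same tracer to about 2.0%.

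Section 3.1.3 lists glucose counter-regulation among the additional exploratory endpoints.

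**The concern.** The tracer is there to separate glucose made by the body from glucose infused, and it can do so only if measured plasma enrichment enters the calculation. In the printed equation it drops out. The result then depends only on glucose concentration, which the clamp sets, and on the sampling interval, which the protocol fixes.

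Section 9.1.2.12 treats endogenous glucose production as the outcome that matters in defence against hypoglycemia, ahead of the hormone levels. Its incremental response is clamp minus basal, and the hypoglycemic-minus-euglycemic difference in that response is tested before versus after transplant by ANOVA at P < 0.05. Applied literally, the rule would combine a tracer-based basal value with a tracer-free clamp value. The Ra part of the hypoglycemic-minus-euglycemic difference would be nearly the same constant for every subject at both times.

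**Working it through.** **Inputs, all from section 9.1.2.12.** F = 0.05 mg/kg/min; V = 40 mL/kg; t2 - t1 = 20 min; C = 0.90 mg/mL (euglycemic) and 0.80, 0.65, 0.55, 0.45 mg/mL (hypoglycemic plateaus); tracer infusate enrichment 0.99; glucose infusate enrichment about 0.02. The protocol states no numerical Ra, so there is no figure to reproduce. It gives neither plasma enrichment nor glucose infusion rate (GIR); values of these below are assumptions.

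**1. Algebra.** Write Cm for (C2+C1)/2 and dt for t2 - t1. The factor (E2-E1) cancels:

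- Reading A, left to right: Ra = F - V·Cm/(2·dt)
- Reading B, final /2 in the denominator: Ra = F - 2·V·Cm/dt

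No E remains in either. If E1 = E2, the printed expression is 0/0.

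**2. Numbers at dt = 20 min.** At 90 mg/dL, V·Cm = 40 × 0.90 = 36. Reading A gives 0.05 - 36/40 = -0.85. Reading B gives 0.05 - 72/20 = -3.55.

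| Glucose (mg/dL) | Ra, reading A (mg/kg/min) | Ra, reading B (mg/kg/min) |
|---|---|---|
| 90 | -0.85 | -3.55 |
| 80 | -0.75 | -3.15 |
| 65 | -0.60 | -2.55 |
| 55 | -0.50 | -2.15 |
| 45 | -0.40 | -1.75 |

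Four different pairs of E1 and E2 gave identical results. For Ra to reach zero at 20 minutes, glucose would have to be 5 mg/dL or less (A: 2 × 0.05 × 20/40 = 0.05 mg/mL) or 1.25 mg/dL or less (B: 0.05 × 20/80 = 0.0125 mg/mL). Clamp EGP subtracts a non-negative GIR, so it is negative too.

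**3. Effect on the planned contrast.** At the 45 and 90 mg/dL targets, the hypoglycemic-minus-euglycemic difference in Ra is -0.40 + 0.85 = +0.45 (A) or -1.75 + 3.55 = +1.80 (B), whatever the tracer shows.

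**4. Changing only the sign is not enough.** If the last (E2-E1) is read as (E2+E1), then Ra = F - V·Cm·[(E2-E1)/dt]/[(E2+E1)/2]. At steady enrichment this is Ra = F = 0.05 for every enrichment, because F is still undivided.

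**5. The form that tracer balance requires.** The tracer pool is V·C·E. Tracer enters at F_total and leaves with glucose at enrichment E. Combining this with the balance for total glucose gives V·C·(dE/dt) = F_total - Ra·E, so

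Ra = {F_total - V·Cm·(E2-E1)/dt} / [(E2+E1)/2].

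**6. Check against the basal formula.** With no glucose infusion, F_total = 0.05 × 0.99 = 0.0495. At steady state:

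| Assumed plasma enrichment | Ra = 0.0495/E | Basal EGP = 0.05(0.99/E - 1) |
|---|---|---|
| 1% | 4.95 | 4.90 |
| 1.5% | 3.30 | 3.25 |
| 2% | 2.475 | 2.425 |
| 3% | 1.65 | 1.60 |

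Ra exceeds basal EGP by exactly IR = 0.05 throughout. The two agree once the tracer infusion is subtracted from Ra.

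**7. The enriched glucose infusion.** During the clamp, F_total = 0.0495 + 0.02·GIR. At an assumed 2% plasma enrichment, Ra = 2.475 + GIR, so Ra - GIR - 0.05 = 2.425 at any GIR. If F_total is held at 0.0495, the same step gives 2.425 - GIR, which is negative for any GIR above 2.425. Over assumed enrichments of 1% to 3%, that limit runs from 4.90 to 1.60 mg/kg/min.

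**The case against.** The strongest defence is that the intent is plain. The protocol names the method and defines C, V, F, E and t, and an analyst who knows tracer work would probably program a sound version. A literal result, negative throughout, would be noticed at once. The text is also a machine reading of a PDF with other damaged notation nearby, so a sign or bracket may have been lost. This stands as a reason for moderate weight and for checking the equation against the source file. It does not clear the text: the plus sign in (C2+C1) survived, the brackets balance, and a restored plus sign would still leave F undivided.

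A second objection concerns the remedy. Dividing by mean enrichment while keeping F at 0.05 would leave out the tracer carried by the glucose infusion, and clamp EGP could still come out negative (step 7). This stands in full and shapes the fix.

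A reader might also infer more than the documents support:

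- That Ra is negative whatever the tracer data. This is not exact: with equal enrichments the expression is undefined, and the enriched glucose infusion is meant to limit changes in enrichment.
- That there is one correct value, such as 2.5 mg/kg/min at 2% enrichment. The protocol's 2% describes the glucose infusate; plasma enrichment is not given.
- That the trial's main conclusions are at risk. The primary and secondary endpoints, basal EGP, and the hormone and symptom responses do not use this equation.

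**Conclusion.** The equation is wrong as written. Enrichment cancels, F is never divided by enrichment, and Ra is negative at every clamp target with 20-minute sampling: -0.85 to -0.40 or -3.55 to -1.75 mg/kg/min, depending on how the final /2 is read. It is undefined when E1 = E2, and it cannot be reconciled with the basal formula in the same section. These results use only the protocol's figures. The comparison values of 4.95 to 1.65 mg/kg/min rest on an assumed plasma enrichment of 1% to 3% and no glucose infusion.

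The reach is limited to clamp EGP and the before-versus-after comparison built on it, which is exploratory. The protocol fixes this formula itself and no corrected version was found elsewhere in it, so it should be put right before anyone programs it.

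**What to change.** Replace the printed equation in section 9.1.2.12 by

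Ra = {F_total - V[(C2+C1)/2][(E2-E1)/(t2-t1)]} / [(E2+E1)/2],

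with these definitions:

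- F_total is all tracer entering: the constant infusion (0.05 mg/kg/min × its 99% enrichment) plus the glucose infusion rate × its enrichment (about 2.0%, preferably as measured).
- Units: V in mL/kg, C in mg/mL, t in minutes, rates in mg/kg/min, and all enrichments on the same scale.
- Clamp EGP = Ra - glucose infusion rate - tracer infusion (0.05 mg/kg/min), so that it equals the basal formula at steady state.

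Label any numerical benchmark with the plasma enrichment it assumes. The cost is one equation and a few lines of definitions. No new samples are needed, provided the glucose infusion rates and the infusate enrichment are recorded.

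### The clamp calculation of glucose appearance counts only the constant tracer infusion and omits the tracer in the enriched glucose infusion, so exploratory clamp EGP is understated by an amount that grows with the glucose infusion rate

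*Protocol*

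**What the plan says.** All of this is in protocol section 9.1.2.12, Glucose Counter-Regulation.

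- **Constant tracer.** Deuterated glucose ("99% enriched; Cambridge Isotopes") is given as a 5-minute prime from t = -120 min and then as a "continuous (0.05 mg/kg·min for 355 min") infusion.
- **Tracer in the glucose infusion.** To limit swings in plasma enrichment, "the variable glucose infusion will be enriched to ~ 2.0 % with" the same deuterated glucose.
- **Targets.** The hypoglycemic clamp uses this infusion "to achieve hourly glucose plateaus of 80, 65, 55, and 45 mg/dL". The euglycemic clamp is run in the same way, with "target glucose 90 mg/dL for the entire 240 min study".
- **Ra.** For the modified Steele equation during the clamps, the Calculations paragraph states "F is the infusion rate (0.05 mg/kg·min").
- **EGP.** "EGP during the clamps will be calculated from the difference between the rate of appearance of glucose in the plasma and the glucose infusion rate".
- **Use of the result.** The increment over basal in the last 20 minutes is formed for each clamp. The hypoglycemic-minus-euglycemic difference is then compared within subject from before to after transplant, two-tailed at P < 0.05.

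Section 3.1.3 lists these clamps among the additional exploratory endpoints.

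**The concern.** In Steele's method Ra is tracer input divided by plasma enrichment, with a correction for changing enrichment. Plasma enrichment reflects every labelled molecule infused, so F has to be the total tracer input. The protocol instead carries the pre-clamp pump rate into the clamp, although its own procedure adds a second tracer source at t = 0. No other sentence in the section adds that source to F or corrects for it later.

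The rationale in the same section presents endogenous glucose production as the response that matters most for defence against hypoglycemia, ahead of the hormone levels. An error that depends on how much glucose was infused falls on the quantity the paired clamps were designed to measure. It also need not be equal in the two clamps being subtracted.

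**Working it through.** **1. The protocol's figure.** Prime plus infusion is 5 + 355 = 360 min, which is t = -120 to t = +240. The 0.05 mg/kg/min is therefore the constant pump rate, and it runs through the whole clamp. It equals total tracer input only if GIR = 0.

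**2. Inputs.** Constant tracer 0.05 mg/kg/min and variable infusate enrichment 0.02 are from the protocol. GIR and true EGP are **assumed**, because the protocol gives neither. The standard Steele form is assumed too; at steady state it reduces to Ra = F/E. All rates are in mg/kg/min.

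**3. Formulas.**
- Tracer input T = 0.05 + 0.02 × GIR
- Share omitted = 0.02 × GIR / T
- Plasma enrichment E = T / (0.05 + GIR + EGP)
- EGP by the protocol's rule = 0.05/E - GIR
- Corrected EGP = T/E - GIR - 0.05

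**4. One clamp, true EGP assumed 0.5.**

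| GIR | T | Share omitted | EGP by protocol rule | Error |
|---|---|---|---|---|
| 1 | 0.07 | 29% | 0.05/0.07 × 1.55 - 1 = 0.11 | -0.39 |
| 2 | 0.09 | 44% | 0.05/0.09 × 2.55 - 2 = -0.58 | -1.08 |
| 4 | 0.13 | 62% | 0.05/0.13 × 4.55 - 4 = -2.25 | -2.75 |
| 6 | 0.17 | 71% | 0.05/0.17 × 6.55 - 6 = -4.07 | -4.57 |
| 8 | 0.21 | 76% | 0.05/0.21 × 8.55 - 8 = -5.96 | -6.46 |

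The corrected formula returns 0.5 in every row. Allowing for 99% tracer purity moves these entries by less than 0.01. The error is -0.02 × GIR/E + 0.05. The small +0.05 arises because the clamp rule does not subtract the constant tracer's own mass, whereas the basal formula does. It outweighs the omission only when GIR is close to zero.

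**5. Two clamps on one occasion (assumed values).**
- Euglycemic GIR 6, EGP 0.2: 0.05/0.17 × 6.25 - 6 = -4.16.
- Hypoglycemic GIR 2, EGP 1.0: 0.05/0.09 × 3.05 - 2 = -0.31.
- Computed difference 3.86; true difference 0.80.

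With EGP 0.5 in both clamps and GIR 6 versus 3, the true difference is 0. The rule gives -4.07 and 0.05/0.11 × 3.55 - 3 = -1.39, a difference of 2.69 before rounding. With the same GIR and the same EGP in both clamps, the error cancels. With the same GIR but different EGP, the true difference is multiplied by 0.05/T, for example 0.05/0.15 = 0.33 at GIR 5.

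**6. Not a steady-state artefact.** A one-pool simulation over 240 min used V = 40 mL/kg, the protocol's glucose targets, and assumed disposal and EGP profiles. It gave GIR 5.85 (euglycemic) and 1.76 (hypoglycemic) over t = 220 to 240. True EGP was 0.30 and 1.29, a difference of 0.99. The standard Steele equation with F = 0.05 gave -3.99 and 0.08, a difference of 4.07. With F as total tracer and the constant tracer subtracted, it returned 0.30 and 1.29.

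**7. Before versus after.** If GIR and EGP are unchanged in both clamps, the error is the same on both occasions and drops out. Suppose instead that euglycemic GIR rises from 5 to 7 with EGP steady at 0.2 and nothing else changes. Computed EGP moves from 0.05/0.15 × 5.25 - 5 = -3.25 to 0.05/0.19 × 7.25 - 7 = -5.09. The tested difference gains 1.84 with no true change. Section 9.1.2.8 says that insulin sensitivity may improve after transplant, so a shift in GIR is plausible, but its size is not known.

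**The case against.** **The endpoint is minor, and the numbers are assumed.** Both are true. The clamps are exploratory, and EGP is one of eight responses calculated from them. The other seven (C-peptide, glucagon, growth hormone, cortisol, epinephrine, norepinephrine and symptom score) do not use F. Basal EGP is also unaffected, because the variable infusion has not started. No primary, secondary, safety or stopping decision depends on clamp EGP. The results can be recalculated later if GIR and enrichment data are kept.

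**The single-occasion difference is not what is tested.** This stands. A reader might infer from 3.86 against 0.80 that the before/after comparison is wrong by a similar amount. The protocol does not support that: only error that changes with GIR or EGP survives the within-subject comparison.

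**The equation as printed is not Steele's.** As it reads, F is not divided by enrichment, and the denominator has E2 - E1 where the standard form averages the two. This may be a conversion fault in the text and is not held against the plan. The figures above therefore rest on the standard form, which the protocol names. The omitted tracer source does not depend on the layout.

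**The laboratory may have used total tracer in practice.** Possibly, but the protocol fixes a number for F, and that number conflicts with its own infusion procedure.

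**Conclusion.** The point holds. As written, F leaves out the tracer in the enriched glucose infusion. Ra is then too low whenever glucose is infused, and clamp EGP is too low at any appreciable GIR. The direction within each clamp follows from the protocol, given the standard Steele equation. The size does not: it depends on GIR, and the 29% to 76% of tracer omitted is for an assumed GIR of 1 to 8 mg/kg/min.

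Unequal GIR is expected, since the same insulin infusion is used at 90 and at 45 mg/dL in the closing interval, but this is an inference from the targets. If euglycemic GIR is clearly the higher, the computed counter-regulatory EGP response is overstated. The before/after test is distorted to the extent that GIR or EGP changes after transplant.

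A reader might go further and conclude that negative EGP values are certain, that the counter-regulation results as a whole are unsound, or that the trial's main conclusions are touched. The documents support none of these. The effect is confined to the exploratory clamp EGP response, and correcting the text before those data are analysed removes it.

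**What to change.** In the Calculations paragraph of section 9.1.2.12:

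1. Define F for each sampling interval as F(t) = constant tracer rate + (enrichment of the variable infusate × GIR(t)). Use the measured enrichment of that infusate or, if it is not assayed, the enrichment as prepared.
2. Define clamp EGP = Ra - GIR - constant tracer rate. Subtract only the constant rate. The tracer in the variable infusion is already inside GIR, and subtracting it again would remove 0.02 × 6 = 0.12 mg/kg/min too much at GIR 6.
3. Check the printed Ra equation against the standard Steele form.

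This costs a few lines of text, with no change to the infusions, visits or sampling. GIR is already needed for EGP. Measured enrichment of the variable infusate may be an added assay: the protocol gives only a nominal 2%, and the infusate enrichment in its basal formula is that of the constant tracer.
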